11.1. Analysis Set

The Treated Population will consist of all subjects who receive at least 1 dose of study drug. Primary efficacy and safety analyses will be performed using the Treated Population. The intent-to-treat (ITT) population will consist of all subjects who are randomized.

The PK/PD Population will consist of all subjects who received at least 1 dose of study drug and had at least 1 sample collected during treatment to determine the drug concentration or pharmacodynamic biomarker response.

The treatment arms will be evaluated independently. Continuous variables will be summarized using descriptive statistics such as mean, median, standard deviation (SD), 25th/75th percentiles, and range. Categorical variables will be summarized using frequency tables. For time-to-event variables, the Kaplan-Meier method will be used for descriptive summaries.

11.2. Sample Size Determination

The study was originally designed to enroll approximately 200 subjects (approximately 100/arm). On the basis of historical data, the outcomes are poor for patients whose disease is relapsed after or refractory to JAK inhibitor therapy. The expected spleen response rate (proportion of subjects who achieve $\geq 35\%$ reduction in spleen volume at Week 24) and symptom response rate (proportion of subjects who have $\geq 50\%$ reduction in TSS at Week 24) in patients with salvage therapy or without treatment

For each treatment arm, the sample size is calculated based on the following assumptions:

1.	null hypothesis:
2.	alternative hypothesis:
3.	the null hypothesis is tested by the intersection-union test. ⁶ Each of the co-primary endpoints is tested at one sided α =0.025, and the maximum Type I error rate for testing co-primary endpoints is the same as one sided α =0.025

The original study design allowed for enrollment of approximately 200 subjects; however, following the first interim review of data, and in line with Protocol Amendment 2, enrollment of new subjects into Arm A was suspended and enrollment into Arm B was permanently closed. Therefore, total enrollment in the study may be approximately 160 subjects if enrollment in Arm A is resumed after the second interim review.

11.3. Subject Information

The number of subjects enrolled, dosed, and discontinued will be summarized. Treatment discontinuation will be summarized according to the reasons for discontinuation.

Demographic and baseline vital sign variables will include age, sex, race, ethnicity, height, weight, blood pressure, and weight. Baseline disease characteristics (documented in the source documents and CRFs) will be summarized.

11.4. Efficacy Analyses

Planned efficacy analyses are as follows: (1) a first interim review after approximately 20 subjects in each arm have been followed for at least 12 weeks; (2) a second interim review with a clinical cutoff that is 6 months after the clinical cutoff used for the first interim review; (3) the primary efficacy analysis after all subjects have been followed for at least 24 weeks; (4) the final analysis at the end of the main study, which is defined as 18 months after the last subject is enrolled or when the sponsor terminates the study; and (5) OS-related analysis will be performed or updated when the Extension Phase has ended.

Primary Endpoint Analyses

The analysis for the co-primary endpoints (spleen response rate and symptom response rate) will be based on the Treated Population. For each treatment arm, spleen response rate and symptom response rate will be presented along with their 95% 2-sided exact confidence interval. Sensitivity analysis may be performed on the intent-to-treat population and evaluable population in support of the primary analysis if deemed appropriate.

Spleen response rate is defined as the proportion of subjects who achieve ≥35% reduction in spleen volume at Week 24 from baseline as measured by imaging scans. The spleen response data reviewed by the IRC will be used for the interim data reviews, the primary analysis, and the final analysis. The response data assessed by the investigators will be used as a supportive analysis.

Symptom response rate is defined as the proportion of subjects who have \geq 50% reduction in TSS at Week 24 from baseline as measured by the modified MFSAF v2.0 diary. The TSS will be calculated as the 7-day average of daily TSS, which is the summation of 6 individual symptom scores (night sweats, itchiness, abdominal discomfort, pain under ribs on left side, early satiety, bone or muscle pain).

Secondary Endpoint Analyses

- Proportion of subjects with CR or PR, and proportion of subjects with CI will be evaluated using the same statistical methods as for the primary endpoints.
- Proportion of subjects with spleen response, symptoms response, and anemia response per modified 2013 IWG-MRT criteria will be reported along with a 95% confidence interval.
- The distributions of duration of spleen response and duration of symptom response will be summarized using Kaplan-Meier estimates based on responding subjects. The estimated median will also be reported along with a 95% confidence interval. Duration of CR or PR, CI, and anemia response will be provided descriptively using similar methods based on responding subjects.
- The distribution of OS will be summarized using similar Kaplan-Meier methods.
- Change in spleen volume, change in TSS, and change in PRO endpoints from baseline will be descriptively summarized over time.
- Additional analyses to be performed for the subjects who were initially treated with 4.7 mg/kg and subsequently dose escalated to 9.4 mg/kg per the guidance outlined in Section 6.

11.5. Pharmacokinetic Analyses

Pharmacokinetic Blood Sample Collection

Pharmacokinetic data collected from the sparse and intensive PK sampling will be pooled for the analysis. Nonlinear mixed effects modeling using NONMEM software will be used to develop the population PK model in MF subjects. Different structural and random effects models will be considered and compared. A stepwise covariate model building strategy will be adopted and covariate effects on PK parameters will be explored. Diagnostic plots, summary statistics, and a comparison of raw data to model predictions will be evaluated.

Serial Pharmacokinetic Blood Sample Collection

Data will be listed for all subjects with available plasma concentrations per treatment. Subjects will be excluded from the PK analysis in situations where extenuating factors preclude an accurate assessment of the PK parameters of interest (eg, incomplete administration of the study drug; concentration data not sufficient for PK parameter calculation due to missing PK draws at multiple visits; or early discontinuation from the study).

All plasma concentrations below the lowest quantifiable concentration or missing data will be labeled as such in the concentration data presentations. Concentrations below the lowest quantifiable concentration will be treated as zero in the calculation of PK parameters and for the calculation of summary statistics of concentration-time data as per the PK analysis guideline. All subjects and samples excluded from the analysis will be clearly documented in the Clinical Study Report.

Mean and individual plasma concentrations of imetelstat versus time profiles will be plotted. Descriptive statistics of imetelstat, including arithmetic mean, SD, coefficient of variation, geometric mean (PK parameters only), median, minimum, and maximum will be calculated for the imetelstat plasma concentrations at each sampling time for imetelstat and for all PK parameters of imetelstat.

11.6. Immunogenicity Analyses

The incidence of antibodies to imetelstat will be summarized for all subjects who receive at least 1 dose of imetelstat and have appropriate samples for detection of antibodies to imetelstat (ie, subjects with at least 1 sample obtained after administration of at least one dose of imetelstat). The results will be summarized by treatment arm and subjects with appropriate samples for the detection of antibodies to imetelstat.

11.7. Pharmacokinetic/Pharmacodynamic Analyses

Different PK/PD models will be built to understand and characterize the exposure-response relationship for key efficacy and safety parameters, to detect the influence of covariates, and identify inter-individual variability in response. The exposure-response analysis for efficacy parameters includes SVR from baseline at Week 12 and the proportion of subjects with response (≥35% SVR from baseline at Week 12). The exposure-response analysis for safety parameters will characterize the time course of platelet counts and hemoglobin. If sufficient data are available, then the immunogenicity effect on imetelstat PK and exposure–response relationships for efficacy and safety will be assessed and the correlation between the exposure and the change of biomarkers will be explored. The details will be given in the modeling analysis plan. If sufficient PD biomarker data are available, then the correlation between exposure and the change of PD will be explored.

11.8. Biomarker Analyses

Biomarker measures and the change from baseline will be listed, tabulated, and plotted where appropriate. Subjects may be grouped by dose, or clinical response. Correlation of baseline or changes of biomarkers with clinical parameters will be analyzed by appropriate statistical methods (eg, parametric or non-parametric, univariate or multivariate).

Results of biomarker analyses may be presented in a separate report. Planned analyses are based on the availability of clinically valid assays and may be deferred if emerging study data show no likelihood of providing useful scientific information.

11.9. Safety Analyses

Safety analyses will be performed using the Treated Population. Safety will be evaluated using the NCI-CTCAE (Version 4.03). The safety parameters to be evaluated are the incidence, intensity, and type of adverse events, clinically significant changes in the subject's physical examination findings, vital signs measurements, clinical laboratory results (hematology and chemistry), and deaths. Exposure to study treatment and reasons for discontinuation will be tabulated. Safety

variables are to be tabulated by descriptive statistics (n, mean, median, SD, minimum, and maximum; or n and percent).

Additional analyses will be performed for the subjects who were initially treated with imetelstat 4.7 mg/kg and subsequently dose escalated to 9.4 mg/kg per the guidance outlined in Section 6.

Adverse Events

Treatment-emergent adverse events are adverse events that occur after the first dose of study drug, through the Treatment Phase, and for 30 days following the last dose of study drug; any adverse event considered study drug-related regardless of the start date of the event; or any event that is present at baseline but worsens in severity or is subsequently considered drug-related by the investigator. The number and percent of subjects with treatment-emergent adverse events will be summarized according to intensity (NCI-CTCAE, Version 4.03) and drug relationship as well as categorized by System Organ Class and preferred term by treatment arm.

The verbatim terms used in the CRF by investigators to identify adverse events will be coded using the Medical Dictionary for Regulatory Activities (MedDRA). Treatment-emergent adverse events are adverse events with onset during the treatment phase or that are a consequence of a pre-existing condition that has worsened since baseline. All reported adverse events will be included in the analysis. For each adverse event, the percentage of subjects who experience at least 1 occurrence of the given event will be summarized by treatment arm.

Clinical Laboratory Tests

Laboratory data will be summarized by type of laboratory test. Reference ranges and markedly abnormal results (specified in the Statistical Analysis Plan) will be used in the summary of laboratory data. Descriptive statistics will be calculated for each laboratory analyte at baseline and for observed values and changes from baseline at each scheduled time point.

Parameters with predefined NCI-CTCAE toxicity grades will be summarized. A summary of the shifts in selected laboratory hematology and serum chemistry parameters from baseline to the worst toxicity grade experienced by the subject during treatment will be provided. The worst toxicity grade during the study will be tabulated.

Electrocardiogram (ECG)

Electrocardiogram data will be listed by ECG parameter at Screening.

Vital Signs

Descriptive statistics of temperature, heart rate, respiratory rate, and blood pressure (systolic and diastolic) values and changes from baseline will be summarized. The percentage of subjects with clinically important changes from baseline will be summarized.

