All laboratory tests should be performed at the laboratory facilities associated with the investigational site. Laboratory certificates or accreditation and normal ranges of the laboratory facility at the site must be submitted to the sponsor before the enrollment of any subject at the site. If the subject has the laboratory assessments conducted at a laboratory facility other than the one associated with the investigational site, then the investigator must submit to the sponsor laboratory certificates or accreditation and normal ranges for that facility as well. The laboratory reports must be filed with the source documents.

Blood samples for serum chemistry and hematology to assess the safety of study treatment will be collected. Required laboratory tests must be performed within 48 hours prior to the scheduled visit. For Cycle 1, Day 1 only, clinical laboratory tests do not need to be repeated if the Screening tests were performed within 5 days of the first dose of study treatment.

The investigator must review the laboratory report, document this review, and record any clinically relevant changes occurring during the study in the adverse event section of the CRF. For example,

laboratory abnormalities leading to an action regarding any study treatment (dose reduction, temporary stop, delay of the start of a cycle or permanent stop) or the start of concomitant therapy should be reported. For each laboratory abnormality reported as an adverse event, the following laboratory values should be reported in the laboratory section of the CRF: the value indicative of the onset of each toxicity grade; the most abnormal value observed during the adverse event, and the value supporting recovery to Grade ≤ 1 or to baseline values.

The following tests will be performed by the local laboratory at the time points shown the Time and Events Schedule:

• Hematology Panel

-hemoglobin

-absolute neutrophil count (ANC)

-manual percent immature myeloid cells (blasts, promyelocytes, myelocytes, metamyelocytes and nucleated RBC) -white blood cell (WBC) count

-platelet count

• Serum Chemistry Panel

-sodium

-potassium

-blood urea nitrogen (BUN)

-creatinine

-alanine aminotransferase (ALT)

- total bilirubin (with fractionation at screening; with fractionation post-screening if

total bilirubin is abnormal)

-alkaline phosphatase (ALP)

-lactic acid dehydrogenase (LDH)

-albumin

-serum ferritin

-aspartate aminotransferase (AST)

• INR (or PT) and aPTT

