2.3.9.3. Clinical Laboratory Tests

Laboratory data of hematology and clinical chemistry up to 30 days after last dose will be reported in SI units.

Summary statistics (N, mean, SD, median, and range) will be calculated for the raw data and for their changes from baseline by scheduled visits, as well as for last value and for the changes from baseline to the last value. Within a cycle, summary statistics from the worst values will be provided. Individual values outside the normal ranges will be identified (by “H” for high and “L” for low) in the data listings displaying the absolute values for each subject.

Displays of over-time summaries will be presented for the following key laboratory parameters: hemoglobin, white blood cell count, absolute neutrophil count, platelet count, manual percent immature myeloid cells (blasts, promyelocytes,

myelocytes,metamyelocytes and nucleated RBC), sodium, alkaline phosphatase, potassium, lactic acid dehydrogenase, blood urea nitrogen, albumin, creatinine, serum ferritin, alanine aminotransferase (ALT), aspartate aminotransferase (AST), total bilirubin (with fractionation if abnormal), INR(or PT) and aPTT • INR (or PT) and aPTT.

Shift tables for each cycle will be produced for selected laboratory parameters, to include hemoglobin, white blood cell count, neutrophils, platelet count, creatinine, total bilirubin, ALT, AST, lactic dehydrogenase, sodium, and potassium. These tables will summarize by cycle the number of subjects with each baseline CTC grade and changes to the maximum CTCAE grade in the cycle. For laboratory parameters without CTCAE grade, shifts from baseline to highest per cycle (Low, Normal, High) categories will be used.

Shift tables from baseline to worst value on treatment (from treatment start to 30 days after last dose or the end of treatment visit date, whichever is later) will also be provided. The worst toxicity grade during the treatment will be tabulated.

In addition, incidence of persistent (≥ 2 or 4 weeks) and severe (≥ 3 or 4 grade) cytopenia (thrombocytopenia/neutropenia) will be evaluated. Maximum post-baseline CTCAE grade for anemia, leukopenia, neutropenia, and thrombocytopenia will be tabulated.

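### Continuous liver-test summaries pool raw local-laboratory values in SI units; AST, ALT, ALP and total bilirubin should also be shown as multiples of the reporting laboratory's ULN, and ALP added to the by-cycle shift tables

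*Protocol*

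**What the plan says.** **Where the tests are run.** Protocol 9.8: "All laboratory tests should be performed at the laboratory facilities associated with the investigational site". The panels, including AST, ALT, ALP, total bilirubin and LDH, follow the sentence "The following tests will be performed by the local laboratory at the time points shown the Time and Events Schedule". The section also foresees a second laboratory for one subject: "If the subject has the laboratory assessments conducted at a laboratory facility other than the one associated with the investigational site", the investigator must supply that facility's accreditation and normal ranges too.

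**How the results are summarized.** Protocol 11.9: "Descriptive statistics will be calculated for each laboratory analyte at baseline and for observed values and changes from baseline at each scheduled time point". SAP 2.3.9.3: "Summary statistics (N, mean, SD, median, and range) will be calculated for the raw data and for their changes from baseline by scheduled visits". The SAP adds last values, worst values within a cycle and over-time displays of key parameters, ALP among them. The only harmonization it states is this: "Laboratory data of hematology and clinical chemistry up to 30 days after last dose will be reported in SI units".

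**What is referenced to a normal range.** Protocol 11.9 promises: "Reference ranges and markedly abnormal results (specified in the Statistical Analysis Plan) will be used in the summary of laboratory data". In SAP 2.3.9.3 this becomes high/low flags in listings, shifts by CTCAE grade, and Low/Normal/High shifts for ungraded analytes. No criteria for markedly abnormal results are given. The by-cycle shift list names total bilirubin, ALT, AST and LDH but not ALP. A separate shift from baseline to worst on-treatment value, and a table of worst grade, are planned without a restricted list.

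Neither document plans a summary in multiples of ULN.

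**The concern.** SI conversion aligns units. It does not align methods or reference ranges. The trial's own liver limits are set in multiples of ULN: the eligibility limits (inclusion criterion 9.1), the laboratory conditions for dose escalation (Protocol 6), the events of interest (9.8, 12.3.3.1) and the limits for repeat testing (9.8). The continuous tables therefore use a different scale from the one on which the trial defines hepatic risk.

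Liver tests are the trial's adverse events of interest. Protocol 1.1.5.3.3 reports that in the previous myelofibrosis study most liver-test abnormalities were Grade 1 or 2, and that the long-term consequences are unknown. Gradual movement below Grade 3 is thus worth seeing clearly, and by-visit continuous tables are a natural place to see it. At stake is the readability of those tables.

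**Working it through.** The documents state no figure on this point, so there is none to reproduce. The calculations below are illustrations. Only the 107 subjects (SAP 1.4) come from the documents. ULN ratios, variances, site count and drop-out are assumptions.

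**1. Spread.** *Two laboratory groups.* Every subject is constantly at 2 x ULN, half in laboratories with ULN = U and half with ULN = rU. The raw values are 2U and 2rU, the mean is U(1 + r), the SD is U(r - 1), and CV = (r - 1)/(r + 1).
- r = 1.2: 0.2/2.2 = 9%
- r = 1.5: 0.5/2.5 = 20%
- r = 2.0: 1/3 = 33%

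This has no biological variation, so it overstates the relative effect.

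*With biological variation.* Let sw be the between-subject log-SD on the ULN scale and sl the between-laboratory log-SD of ULN. Then SD(log raw)/SD(log xULN) = sqrt(sw² + sl²)/sw.

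| sw | sl = 0.1 | 0.2 | 0.3 | 0.4 |
|---|---|---|---|---|
| 0.4 | 1.03 | 1.12 | 1.25 | 1.41 |
| 0.6 | 1.01 | 1.05 | 1.12 | 1.20 |
| 0.8 | 1.01 | 1.03 | 1.07 | 1.12 |

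**2. Weighting of a real rise.** A rise of 1 x ULN adds U in one group and rU in the other. At 50:50 the high-ULN group supplies r/(1 + r) of the mean raw change: 55%, 60% and 67% for r = 1.2, 1.5 and 2.0.

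**3. Switching laboratory.** A subject constant at 2 x ULN who moves from ULN U to ULN 1.5U goes from 2U to 3U, an apparent rise of 50%. In general the apparent change is r - 1.

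**4. Observed mean when the laboratory mix changes.** In the two-group case, let the high-ULN share go from 50% to 70%. The raw mean changes by (0.3 + 0.7r)/(0.5 + 0.5r) - 1.
- r = 1.2: 1.14/1.10 - 1 = 3.6%
- r = 1.5: 1.35/1.25 - 1 = 8.0%
- r = 2.0: 1.70/1.50 - 1 = 13.3%

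*Simulation.* 107 subjects, 40 sites, sw = 0.6, within-subject log-SD 0.2, about half dropping out, no true change, 4,000 replicates.

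| sl | mean trend in raw mean, drop-out unrelated to ULN | its SD across replicates | mean trend, drop-out 60% (ULN above median) vs 40% |
|---|---|---|---|
| 0.1 | 0.2% | 7.6% | -1.7% |
| 0.2 | -0.1% | 7.8% | -3.3% |
| 0.3 | 0.2% | 8.4% | -4.6% |
| 0.4 | -0.1% | 9.1% | -6.0% |

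On the ULN scale the mean trend is about 0% and its SD is about 7.5% to 7.6%.

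*Check of the last column.* For lognormal ULNs, the retained weights of 0.4 and 0.6 give a ratio of 1.2 - 0.4Φ(sl). With Φ = 0.540, 0.579, 0.618 and 0.655, the trend is -1.6%, -3.2%, -4.7% and -6.2%, in agreement. The sign depends on which laboratories lose more subjects.

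Unrelated drop-out therefore gives no systematic trend, only somewhat more noise in any one trial.

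**5. Change from baseline.** With one laboratory per subject and no true change, each subject's change is zero whatever the mix, so the figures in step 4 do not apply to it. In the simulation, mean change stayed between 0.0% and 0.2% in every scenario. Letting 10% of subjects switch laboratory at random left that mean near 0% and raised its SD from 4.9% to 5.8% at sl = 0.4.

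**6. What the grade tables cover.** Grade 3 or higher is above 5.0 x ULN for AST, ALT and ALP, and above 3.0 x ULN for bilirubin (9.8, 12.3.3.1), so the grade tables are ULN-based. They show only crossings between bands. Subjects may enter with total bilirubin up to 3 x ULN and ALP up to about 5 x ULN (4.1). In the previous study, worsening also counted a rise to at least 1.5 times an already raised baseline (1.1.5.3.3), so grade change was not its only criterion. As the by-cycle list is written, ALP appears over time only in raw-value summaries, although 2 of that study's 3 subjects with Grade 3 liver tests had ALP elevation.

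**The case against.** The strongest reply is that the hepatic signal does not rest on these tables. Grade shifts, worst grade, range flags and hepatic events of interest are all planned, and an independent hepatic committee reviews all liver-test abnormalities at least quarterly. SAP 2.3.9.1 leaves the layout of the hepatic event tables to Data Presentation Specifications that are not in the documents. Most of this stands, and it is why the point is small. A reader might infer that raw values replace ULN-based summaries altogether; the documents do not support that.

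A reader might also infer that the tables will show false time trends. Steps 4 and 5 show that an observed mean drifts systematically only if leaving the tables is related to laboratory ULN, and nothing in the documents says it is. The laboratory mix can change: besides drop-out, SAP 2.1.3 takes data from dose escalation onward out of the tables, and escalation is at the investigator's discretion. That is not evidence of a link to ULN.

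Three further replies:
- **Comparison of doses.** Arms are evaluated independently, and allocation was randomized until Amendment 2, so there is no systematic reason for laboratory mix to differ by dose among randomized subjects. This stands.
- **Scaling by ULN is not neutral.** If two laboratories use the same assay but set different limits, dividing by ULN adds noise. The near-zero results on the ULN scale follow from assuming purely proportional differences. This stands, and is a reason to add the scale and keep SI units.
- **Central laboratory.** Protocol 17.6 and 17.11 mention data sent from a central laboratory. Section 9.8 names the panels and assigns them to local laboratories, so the specific instruction governs. The general wording should still be reconciled.

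**Conclusion.** The point holds as an improvement to descriptive hepatic safety displays. By-visit, worst-per-cycle and over-time continuous summaries of AST, ALT, ALP and total bilirubin carry between-laboratory differences that SI conversion does not remove. Spread and unequal weighting follow whenever ULN differences reflect measurement differences. The switching artefact needs a switch, and a shift in the observed mean needs a change in laboratory mix. Mean change from baseline is free of spurious trend when each subject stays with one laboratory.

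The size cannot be fixed from the documents because no ULNs are given. Under the assumptions shown, inflation of the log-scale SD is 1% to 20% at a between-subject log-SD of 0.6, and 1% to 41% over the whole grid. A drop-out pattern tied to ULN moves the raw mean by about 2% to 6%. The 3.6%, 8.0% and 13.3% figures are a two-group case for observed means only.

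The primary endpoints and the event-of-interest definitions are unaffected. A reader might infer that a hepatic signal would be missed; with the grade tables and committee review in place, the documents do not support that. LDH is not a hepatic event of interest and is secondary here.

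**What to change.** In Protocol 11.9 and SAP 2.3.9.3:
- Also summarize AST, ALT, ALP and total bilirubin (LDH optional) as multiples of the ULN of the laboratory that reported each result, for observed values, change from baseline, worst value per cycle and over-time displays. State how many results lack a ULN.
- Keep the SI-unit tables and listings.
- Add ALP to the by-cycle shift tables.

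**Cost.** One derived variable, a few extra tables and a sentence or two of SAP text. Local normal ranges are already collected under 9.8. The scale is imperfect where laboratories set different limits for the same assay, which is why the SI tables stay. No clinical rule changes.
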